8.3.2 Analysis of Primary Endpoints

PPVs on a per-patient and per-region-basis of ⁶⁸Ga-PSMA-11 PET for detection of tumor location confirmed by histopathology/biopsy will be calculated and reported along with the corresponding two-sided 95% confidence intervals. The confidence intervals will be constructed using the Wilson score method.

a) Imaging interpretation ⁶⁸Ga-PSMA-11 PET:

PET images will initially be interpreted by a board certified nuclear medicine physician or a board certified radiologist experienced in reading PET at the time of the imaging study at the institution that the study is being performed. These interpretations will not be used for final evaluation. For the data sets included in the analysis for the Primary Endpoint, imaging data will be anonymized and collected at a central site. PET data will be interpreted by three different readers in a random order at separate reading sessions. ⁶⁸Ga-PSMA PET/CT reading training set and guides will be provided and completion of this training will be required for all central review readers.

Visual interpretation:

Regions of suspected disease will be graded on a two-point scale by each reader (0=Negative or 1= Positive). A region will be judged as positive if at least one lesion in this region is visually positive.

- i) Lymph nodes will be considered positive if the ^{68}Ga -PSMA-11 uptake is focal and greater than blood pool (adjacent or mediastinal blood pool). Pelvic lymph nodes will be subclassified according to their localization as follows: R/L obturator, R/L external iliac, R/L internal iliac and other (total of 7 subgroups).
 - ii) Visceral lesions will be considered positive if the ^{68}Ga -PSMA-11 uptake is focal and greater than physiologic background activity of the involvement organ or anatomic site.
 - iii) Bone lesions will be considered positive if the ^{68}Ga -PSMA-11 uptake is focal and greater than physiologic bone marrow.
 - iv) Prostate bed and prostate lesions will be considered positive if the ^{68}Ga -PSMA-11 uptake is focal and greater than physiologic background activity of the involvement organ or anatomic site.
- b) Follow-up Imaging:

All patients will be followed up 3-12 months with conventional imaging (dedicated CT, MRI and/or bone scan). Interpretation of follow-up imaging will be performed by local read. The follow-up conventional imaging should be the same modality/modalities as the initial staging work-up to allow for reproducible and accurate comparisons.

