^{68}Ga -PSMA-11 PET positive findings will be validated as true or false positive as outlined in more detail below. False negative ^{68}Ga -PSMA-11 PET findings cannot be determined as this would require biopsies of ^{68}Ga -PSMA-11 negative but conventional or functional non- ^{68}Ga -PSMA-11 PET positive imaging lesions. Inclusion of such patients however would be violation of the inclusion criteria.

^{68}Ga -PSMA-11 PET validation based on follow-up imaging:

- i) Lymph nodes will be assessed by change in size. ^{68}Ga -PSMA-11 positive lymph nodes will be considered:
 - (1) True positive:
 - If on follow-up imaging within 3-12 months, lymph nodes seen on CT or MRI decrease by more than 30% (for patients undergoing systemic treatment of focal therapy at this site) or increase by more than 20% in short axis diameter (with a minimum of 3 mm in change in size).
 - If patients with solitary lymph node regions show a decrease of PSA by greater than 50% after targeted treatment (i.e. external beam radiation) and the lymph nodes do not change in size (less than 30% decrease or less than 20% increase in short axis diameter).
 - (2) False positive:

- If on follow-up imaging within 3-12 months, sites of initial⁶⁸Ga-PSMA-11 positive lymph node lesions seen on CT or MRI decrease by more than 30% *without* systemic therapy or focal therapy at this site.
 - If ⁶⁸Ga-PSMA-11 positive lymph node lesions do not meet the criteria for above false positive or true positive findings.
- ii) Visceral lesions (non-lymph node soft tissue or organ) will be assessed by change in size. ⁶⁸Ga-PSMA-11 positive visceral lesions will be considered:
- (1) True positive:
- If on follow-up imaging within 3-12 months, visceral lesions seen on CT or MRI decrease by 30% (for patients undergoing systemic treatment of focal therapy at this site) or increase by 20% in largest diameter.
 - If patients with solitary visceral metastasis show a decrease of PSA by greater than 50% after targeted treatment (i.e. external beam radiation) and lesions do not change in size (less than 30% decrease or 20% increase in largest diameter).
- (2) False positive:
- If on follow-up imaging within 3-12 months, sites of initial⁶⁸Ga-PSMA-11 positive lymph node lesions seen on CT or MRI decrease by more than 30% *without* systemic therapy or focal therapy at this site.
 - If ⁶⁸Ga-PSMA-11 positive lymph node lesions do not meet the criteria for above false positive or true positive findings.

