- iii) ⁶⁸Ga-PSMA-11 positive bone lesions will be considered:
- (1) True positive:
- If there was a corresponding positive sclerotic lesion on the CT portion of the ⁶⁸Ga-PSMA-11 PET.
 - If there is focal uptake seen on the baseline bone scan performed within one month of ⁶⁸Ga-PSMA-11 PET.
 - If there is a lesion noted on the initial MRI performed within one month of ⁶⁸Ga-PSMA-11 PET.
 - If within 12 months follow-up CT demonstrates development of sclerosis.
 - If within 12 months follow-up MRI demonstrates a new bone lesion.
 - If within 12 months follow-up bone scan demonstrates new focal uptake.
- (2) False positive:
- If ⁶⁸Ga-PSMA-11 positive bone lesions do not meet the criteria for true positive findings.
- iv) ⁶⁸Ga-PSMA-11 positive prostate bed and prostate lesions will be considered:

(1) True positive:

- If on follow-up imaging within 12 months, lesions seen on CT or MRI decrease by 30% (for patients undergoing systemic treatment of focal therapy at this site) or increase by 20% in largest diameter..
- If patients with prostate bed lesions show a decrease of PSA by greater than 50% after targeted treatment (i.e. external beam radiation) and lesions do not change in size (less than 30% decrease or 20% increase in largest diameter).

(2) False positive:

- If on follow-up imaging within 3-12 months, sites of initial⁶⁸Ga-PSMA-11 positive lymph node lesions seen on CT or MRI decrease by more than 30% *without* systemic therapy or focal therapy at this site.
- If ⁶⁸Ga-PSMA-11 positive lymph node lesions do not meet the criteria for above false positive or true positive findings.

c) Histopathology/Biopsy:

- i) Localization of lesions for histopathology/biopsy will be classified according to the regions in table 1.
- ii) ⁶⁸Ga-PSMA-11 positive findings are aimed to be confirmed by histopathology/biopsy if clinically feasible.
- iii) Histopathological procedures and biopsies will be performed as clinically indicated and as per institutional protocol.

(1) Positive HP/Biopsy: Confirmed sites of metastatic or tumor involvement by histopathology/biopsy will be discussed with the responsible physician/surgeon.

(2) Negative Biopsy: Patients with suspected tumor recurrence on ⁶⁸Ga-PSMA-11 PET with negative histopathology/biopsy will be handled as outlined below:

(a) Lymph nodes:

- For patients undergoing nodal dissection: Patients will be rescanned with dedicated CT or MRI to determine if the suspicious ⁶⁸Ga-PSMA-11 positive node was removed.

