 1. If ⁶⁸Ga-PSMA-11 positive lymph node is still present, a repeat biopsy can be pursued if clinically feasible and applicable, or follow-up using imaging as described above will be performed.
 2. If the corresponding node was removed, then this will be considered a False Positive.
- For patients undergoing needle biopsy: Images of the procedure will be reviewed to determine if the correct node was biopsied.
 1. If the correct node was biopsied, then a negative biopsy will be considered a False Positive.

2. If the incorrect node was biopsied, then follow-up imaging as described above will be performed.
 - (b) Bone lesions: Given the high rate of false negative biopsies for osseous metastases in patients with prostate cancer, patients with negative bone biopsies of PSMA PET positive lesions will be further evaluated:
 - If pathology demonstrates an alternative diagnoses that is known to be PSMA positive (eg Renal Cell Carcinoma metastases, Paget's disease), then this will be considered a False Positive.
 - If pathology is indeterminate, then follow-up imaging as described above will be performed to determine if the lesion is a True Positive or False Positive.
 - (c) Additionally a repeat ^{68}Ga -PSMA-11 can also be obtained, as allowable, in addition to repeat conventional imaging (CT and/or MRI) in cases of negative biopsy to determine if the biopsy was true negative or false negative.
 - (d) Although not routinely performed during standard practice, immunohistochemical staining for PSMA of tumor specimens (primary and lymph node metastases) may be performed, although not required.

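### The residual false-positive rule in section 8.3.2 counts PET-positive lesions without usable follow-up imaging as false positives, which lowers mainly the secondary PPV

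*Combined protocol and SAP*

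**What the plan says.** Section 8.3.2 b) sets a two-way outcome: "PET positive findings will be validated as true or false positive as outlined in more detail below".

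**Nodes.** There are two routes to true positive.
- The first is a size change on CT or MRI at 3-12 months: a decrease above 30% under treatment, or an increase above 20% in short axis, "with a minimum of 3 mm in change in size".
- The second covers a node of stable size (less than 30% decrease or less than 20% increase): "If patients with solitary lymph node regions show a decrease of PSA by greater than 50% after targeted treatment".

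There are also two routes to false positive. One is shrinkage above 30% without therapy, seen on imaging in the window. The other is a residual: "positive lymph node lesions do not meet the criteria for above false positive or true positive findings". The first false-positive rule names follow-up imaging as a condition; the residual does not.

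**Other sites.** The visceral and prostate-bed rules repeat the residual, still worded for lymph nodes. Bone has its own: "positive bone lesions do not meet the criteria for true positive findings". Three of the six bone true-positive criteria use imaging at or near baseline (sclerosis on the CT part of the PET, a bone scan or an MRI within one month).

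**Where the rules feed in.** Section 8.3.3 reports a secondary PPV against histopathology and imaging follow-up. Section 8.3.1 bases the primary analysis on patients with histopathology. Section 8.3.2 c) sends some unresolved biopsies back to the imaging rules, for example: "If the incorrect node was biopsied, then follow-up imaging as described above will be performed".

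**Follow-up.** Section 8.3.2 b) plans conventional imaging for every patient at 3-12 months. Section 3.4 gives one day of follow-up, and the schedule in section 6.1 lists no follow-up CT, MRI or bone scan. The document has no unevaluable class, no rule for missing imaging and no sensitivity analysis for it.

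**The concern.** A false positive should be a PET finding that the reference standard failed to confirm. The residual rule also takes in findings to which the reference standard was never applied. Both nodal true-positive routes need a known change in size, or a known absence of change, so a node without a second scan cannot qualify whatever its true state. The secondary PPV then measures completeness of follow-up as well as accuracy of the tracer. Incomplete follow-up is foreseeable, because the deciding scans lie outside the scheduled visits.

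A second, smaller problem remains even with complete imaging. The 20% and 3 mm conditions do not fit together, so a node can fall between the two true-positive rules and drop into the residual.

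**Working it through.** **Plan figures.** The plan gives no figure for the effect of this rule. The only figure borrowed from it is the 70% PPV hypothesised in section 8.2.1, used as an example of a true value. The number of 75 stated there (50% against 70%, one-sided 0.01, 90% power) comes out close by the normal approximation: [2.326 × √(0.5 × 0.5) + 1.282 × √(0.7 × 0.3)]² / 0.2² = 76.6, so 77. The sample size is not in dispute, and nothing below depends on it.

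**Step 1: effect on the PPV.** Let π be the true PPV, m the share of PET-positive findings with no usable follow-up and nothing else to settle them, and q the share of those that are diseased. Assume that all other findings are classified correctly.
- Present default (unclassifiable = false positive): π − mq
- Excluded from the denominator: (π − mq) / (1 − m)
- All counted as true positive: π − mq + m

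The documents give neither m nor q; both are assumed here.

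**Step 2: missingness unrelated to disease (q = π = 0.70).** The default becomes π(1 − m). Per 100 PET-positive findings, with Wilson 95% intervals:

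| m | Present default | Excluded | All true positive |
|---|---|---|---|
| 10% | 63/100 = 0.63 (0.532-0.718) | 63/90 = 0.70 (0.599-0.785) | 73/100 = 0.73 |
| 20% | 56/100 = 0.56 (0.462-0.653) | 56/80 = 0.70 (0.592-0.789) | 76/100 = 0.76 |

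Each 10 points of m takes 7 points off the reported PPV. At m = 20%, the handling alone moves the estimate over 20 points (0.56 to 0.76).

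**Step 3: unclassifiable findings less often diseased.** Take 70 diseased among 100 and 20 unclassifiable, of which 4 are diseased (q = 0.20). The default gives (70 − 4)/100 = 0.66. Exclusion gives 66/80 = 0.825. The truth is 0.70, so here the default is closer and exclusion overstates.

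**Step 4: the gap in the nodal rules.** Take a solitary nodal region, targeted treatment and a PSA fall above 50%.
- A 6 mm node grows 10% (0.6 mm). This is below 20%, so it counts as stable: true positive by the second rule.
- A 6 mm node grows 2 mm. 2/6 = 33%, above 20% but short of 3 mm, so the first rule fails. It is not below 20%, so the second fails as well. The residual makes it a false positive.
- A 6 mm node grows 3 mm. 3/6 = 50%: true positive by the first rule.

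The class thus goes from true to false and back to true as growth increases. For a node of diameter d, the gap runs from 0.2d up to 3 mm. It closes at d = 15 mm, where 0.2 × 15 = 3 mm.

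**Step 5: reach into the primary PPV.** A positive biopsy does not need the imaging rules. They are reached when a PET-positive node is still present after a dissection with negative histology, when the wrong node was sampled, or when bone pathology is indeterminate. Only the part of these that then lacks usable imaging is affected.

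**The case against.** The strongest reply is that the plan never says that a missing scan makes a false positive. The rules stand under a subheading about validation by follow-up imaging, nodes are to be judged on size change, and imaging is planned for everyone. A node without a second scan could therefore be taken as not validated and outside the rules. That reading is possible, but the text does not state it. The two-outcome sentence and the unconditional residual point the other way, so analysts could differ.

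A second reply is that the default is merely conservative. That would serve if it were declared as such and shown beside an alternative. Step 3 shows that the default can be nearer the truth than exclusion, which is a good reason to keep it as a bound.

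Three further points stand and limit the concern:
- Missing follow-up alone does not make a bone lesion a false positive if it already meets a baseline true-positive criterion.
- Some stable nodes are true positives through the PSA route.
- The 3 mm minimum is a prespecified measurement threshold. The objection is to its poor fit with the 20% condition, not to its strictness.

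A reader might also infer that every stable or sub-threshold node should become unevaluable. The rules do not support that. The only imaging route left to a nodal false positive would be shrinkage above 30% without therapy, and the PPV would be pushed towards 100% by construction.

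**Conclusion.** The concern holds in a limited form. Applied literally, the residual rule turns absent follow-up into false positives and lowers mainly the secondary PPV. With a true PPV of 70%, the reported value is 63% at m = 10% and 56% at m = 20%. This assumes that unclassifiable findings are diseased as often as the rest. If they are diseased less often, the loss is smaller. The shares are assumptions; the documents give none.

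A reader might infer that missing follow-up could pull the trial's main result down to its 50% null. The documents do not support this. That null is stated for the histopathology-confirmed PPV (section 8.2.1), which is analysed in patients with histopathology, and none is stated for the secondary PPV. Nothing suggests that a large share of biopsied lesions would go to imaging and then also lack it.

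Nor would the planned output show a lower PPV at sites with poorer follow-up, since no analysis by site is planned. The effect would be hidden in the pooled estimate.

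The gap in step 4 is a separate defect of the nodal rules and needs no assumption about missing data.

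**What to change.** 1. Add a third class, *not evaluable*, for a PET-positive lesion only when all of these hold: no histopathology result settles it; no baseline true-positive criterion is met; and there is no follow-up imaging in the window set for that site, or the imaging cannot be compared with baseline.
2. Leave this class out of the main secondary PPV and report its count by region.
3. Give two bounds: all such lesions counted as false positive (the present default) and all counted as true positive.
4. Keep lesions that were imaged and met no true-positive criterion as false positives.
5. Reconcile the 20% and 3 mm conditions so that no imaged node falls between the two true-positive rules. One way is to define stable size in the second rule as any change that does not meet the first.
6. While editing, replace the lymph-node wording in the visceral and prostate-bed residual rules. Reconcile the planned 3-12 month imaging with section 3.4 and the schedule in section 6.1.

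The cost is analysis-plan wording, one extra analysis and a smaller denominator for the secondary PPV. Exclusion is not free of bias (step 3), so the bounds should be reported beside the main figure.

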8.3.3 Analysis of Secondary Endpoints

PPVs on a per-patient and per-region-basis of ^{68}Ga -PSMA-11 PET for detection of tumor location confirmed by histopathology/biopsy and conventional imaging follow-up will be calculated and reported along with the corresponding two-sided 95% confidence intervals. The paired McNemar's test will be used to compare the PPVs of ^{68}Ga -PSMA-11 PET imaging to the PPVs of conventional imaging.

Sensitivity, specificity, and NPVs on a per-patient basis of ^{68}Ga -PSMA-11 PET for detection of tumor location confirmed by histopathology/biopsy will be summarized in tabular format. Furthermore, the positive and negative likelihood ratios (LR+ and LR-) will be calculated and reported. Ninety-five confidence intervals of sensitivity, specificity, and NPV will be calculated using the Wilson score method. The comparisons of sensitivity, specificity, and NPV on a per-patient basis of ^{68}Ga -PSMA-11 PET imaging will be compared to of sensitivity, specificity, and NPV on a per-patient basis of conventional imaging using a paired McNemar's test.

Detection rates on a per-patient basis of ^{68}Ga -PSMA-11 PET stratified by PSA value (0.2 - <0.5, 0.5 - <1.0, 1.0 - <2.0, 2.0 - <5.0, 5.0) will be summarized in tabular format and compared between PSA strata using chi-square analysis. The impact of ^{68}Ga -PSMA-11 PET on clinical management in BCR patients will be evaluated using descriptive statistics.

9 Study Management

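### For bone lesions without conclusive histology, the truth rules make PPV largely a measure of agreement with conventional imaging, which is also the comparator in section 8.3.3

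*Combined protocol and SAP*

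**What the plan says.** Section 8.3.2 b) iii) gives six ways for a PET-positive bone lesion to be a true positive. Three use findings already present at baseline:

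- "If there was a corresponding positive sclerotic lesion on the CT portion of the" PSMA scan;
- "If there is focal uptake seen on the baseline bone scan performed within one month of" the PSMA scan;
- "If there is a lesion noted on the initial MRI performed within one month of" the PSMA scan.

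Three need something new on follow-up:

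- on CT, sclerosis that appears by 12 months;
- on MRI, "If within 12 months follow-up MRI demonstrates a new bone lesion";
- on bone scan, focal uptake that was not there before, over the same period.

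Only the CT bullet contains the word *corresponding*. Every bone lesion that meets none of the six is a false positive. There is no not-evaluable class.

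For biopsied bone, section 8.3.2 c) has a separate rule: "If pathology demonstrates an alternative diagnoses that is known to be PSMA positive (eg Renal Cell Carcinoma metastases, Paget's disease", and such a lesion is a false positive. Indeterminate bone pathology is referred back to the follow-up imaging rules.

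Section 8.3.1 limits the primary analysis to patients with histopathology. Section 8.3.3 reports a secondary PPV against histology plus conventional imaging follow-up, and uses a paired McNemar test to "compare the PPVs of" PET and conventional imaging.

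**The concern.** A reference standard should be able to contradict both the test and its comparator. For bone lesions classified by imaging, these rules cannot contradict a baseline bone scan or MRI that agrees with PET, and they always count against PET when conventional imaging never shows the lesion. The resulting PPV says how often conventional imaging shows what PET shows, at baseline or within a year. That is not the same as how often PET is right.

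The two parts of section 8.3.2 also disagree on the same lesion. Biopsy-proven Paget's disease is a false positive. Without a biopsy, the same lesion with focal uptake on a baseline bone scan is a true positive as written.

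At stake are the secondary bone and all-region PPV, the comparison with conventional imaging, and a part of the primary bone PPV. Bone is the largest expected region (35%), only about 25% of patients are expected to have a biopsy (section 8.2.1), and the pooled data are meant to support an NDA (section 1.1).

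**Working it through.** **The plan's own bone figure.** Section 8.2.1 states power above 99% for a bone PPV of 70% against 50%, one-sided 0.01, with 131 biopsies (35% × 375 = 131.25). A one-sample z-test gives Φ((0.20 × √131 − 2.326 × 0.50) / √(0.70 × 0.30)) = Φ((2.289 − 1.163) / 0.458) = Φ(2.46) = 99.3%. The exact binomial test rejects at 80 or more of 131, with size 0.007 and power 98.9%. The figure reproduces. It also shows that the 50% and 70% thresholds belong to the biopsy reference, so below they serve only as a yardstick for the imaging-based PPV.

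**The rules side by side (section 8.3.2 b).**

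| Lesion | Baseline finding confirms | Change on follow-up confirms | PSA fall after targeted treatment confirms | Anything else |
|---|---|---|---|---|
| Lymph node | no | yes | yes, if solitary | false positive |
| Visceral | no | yes | yes, if solitary | false positive |
| Prostate and bed | no | yes | yes | false positive |
| Bone | yes, three routes | yes, three routes | no | false positive |

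(The fallback bullets for visceral and prostate lesions name lymph nodes; I read that as a carry-over.) The default to false positive is common to all types. Bone alone has baseline routes, and bone alone lacks a PSA route.

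**What follows without any rates.** Take PET-positive bone lesions without conclusive histology, and grant that each finding is at the PET site.

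1. Also seen on bone scan or MRI within one month: always a true positive.
2. Sclerotic on the CT of the same scan: always a true positive.
3. Not seen at baseline but new on CT, MRI or bone scan within 12 months: true positive.
4. Never shown: always a false positive.

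PPV is the share in groups 1 to 3, which is the share that conventional imaging (counting the index CT) ever shows. The rules classify PET-positive findings only, so no lesion they classify can make a baseline bone scan or MRI wrong, whereas PET is wrong throughout group 4. More data cannot remove that asymmetry from the section 8.3.3 comparison.

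**Illustrative size, imaging-classified lesions.** Let p be the real PPV, s the share of real metastases that meet a rule, and f the share of other PET-positive bone lesions that meet a rule. Apparent PPV = p·s + (1 − p)·f. The documents give neither s nor f; the values are assumptions.

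| p | s | f | Apparent PPV |
|---|---|---|---|
| 50% | 0.9 | 0.5 | 0.45 + 0.25 = 70% |
| 50% | 0.9 | 0.1 | 0.45 + 0.05 = 50% |
| 70% | 0.9 | 0.5 | 0.63 + 0.15 = 78% |
| 70% | 0.7 | 0.3 | 0.49 + 0.09 = 58% |
| 70% | 0.5 | 0.1 | 0.35 + 0.03 = 38% |
| 90% | 0.5 | 0.1 | 0.45 + 0.01 = 46% |

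The bias is (1 − p)·f − p·(1 − s), which can have either sign.

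**Diluted by histology.** If a share u of bone lesions is classified by imaging, the combined PPV is (1 − u)·p + u·[p·s + (1 − p)·f], taking p as equal in both groups and histology as correct. With u = 75% (the complement of the 25% biopsy rate, assumed to hold for bone), the first row becomes 0.125 + 0.525 = 65% and the last 0.225 + 0.345 = 57%. Section 8.3.1 assigns the remaining patients to the secondary endpoints; read literally, u would be 100%.

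**Primary bone PPV.** Only biopsies referred to imaging are affected. With h the share confirmed on biopsy, i the share of the rest referred, and m the share of those meeting a rule, observed PPV = h + (1 − h)·i·m. At h = 50%:

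- i = 0.25, m = 0.2: 0.5 + 0.5 × 0.05 = 52.5%; the 131-biopsy test rejects with probability 0.03.
- i = 0.5, m = 0.5: 0.5 + 0.5 × 0.25 = 62.5%; it rejects with probability 0.67.

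These are false rejections only if the lesions so confirmed are not metastases. If they are metastases the biopsy missed, the shift is a proper correction.

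**The case against.** The strongest reply is scope. The primary PPV is confirmed by histology in patients who have it, and section 8.3.2 c) gives a reason for using imaging after a negative bone biopsy: such biopsies are often falsely negative. This stands. A reader might infer that bone PPV as a whole, including the primary, measures agreement with conventional imaging; the documents do not support that.

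Other strong readings also fail or weaken:

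- **The index test confirms itself.** PET positivity in bone is defined by uptake above marrow alone. CT sclerosis is a separate morphological finding, though from the same session.
- **Progression elsewhere confirms a false call.** The bullets sit under a stem about the PET-positive lesion, so a site match is the natural reading. The wording does not secure it, since one bullet says *corresponding* and five do not.
- **Other lesions need change and bone does not.** Solitary nodes and visceral lesions, and prostate bed lesions, can be confirmed by PSA fall without size change, and three bone routes do need a new finding.
- **A treated PET-only bone lesion is bound to be a false positive.** It can still be confirmed by a new finding on MRI or bone scan. It fails only if no modality shows it.
- **Indeterminate biopsies are settled with no follow-up.** Section 8.3.2 c) says follow-up imaging will be done. What is unclear is whether the baseline routes also apply.
- **Renal cell metastases.** The exclusion of other malignancy within two years limits these. It does nothing about Paget's disease.

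What remains is the structure: baseline conventional findings as sufficient evidence, a default false positive, and the comparator inside the reference standard.

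**Conclusion.** The concern holds for bone lesions without conclusive histology. It affects the secondary combined-reference PPV for bone and all regions, and the section 8.3.3 comparison, where the lack of independence follows from the rules themselves and needs no assumed rate. The primary bone PPV is affected only through indeterminate biopsies sent to imaging.

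The size is unknown. A reader might infer that the rules flatter PET and lift an unacceptable 50% to the hypothesised 70%. That needs s = 0.9 and f = 0.5 with every lesion classified by imaging; other plausible pairs give no bias or a large downward one. The formulas also work per lesion, while the plan reports PPV per region and per patient. The figures show that the rules can move the result across the plan's own 50% to 70% range, not which way they will.

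**What to change.** 1. In section 8.3.2 b) iii), require every bone bullet to refer to a finding at the PET-positive site that is not attributed to a benign or other-tumour cause.
2. Report the bone and all-region combined-reference PPV with and without lesions confirmed only by baseline imaging, including index-scan CT. In the second analysis treat those lesions as not evaluable, not as false positives.
3. Class as not evaluable any PET-positive bone lesion that lacks adequate follow-up or was treated before it could be verified. Show a sensitivity analysis counting them as false positives.
4. In section 8.3.3, report the bone comparison of PET with conventional imaging against histology alone, next to the combined reference, and state that the combined version is not independent of the comparator.
5. In section 8.3.2 c), state whether the referral of indeterminate bone biopsies to imaging includes the baseline routes. Show the primary bone PPV with and without biopsies resolved by imaging.

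Two simpler repairs should be avoided. Deleting the index-CT bullet alone would push lesions already sclerotic at baseline, which cannot develop sclerosis, into the default false-positive class unless another route applies. Dropping baseline-confirmed lesions from the comparison would remove concordant true positives and keep the default false positives.

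The cost is wording, a few extra tabulations and a wider bone interval in the restricted analyses. Local readers would have to record the site and attributed cause. No new scans are needed. The rules should be settled before lesions are classified, since later changes would look driven by results.

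### A non-sclerotic bone lesion seen only on a bone scan or MRI more than one month from PET has no true-positive route when it grows, and defaults to false positive

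*Combined protocol and SAP*

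**What the plan says.** Section 8.3.2 b) iii) of the combined protocol and SAP lists six sufficient conditions for a true-positive bone lesion:

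- Index CT: "If there was a corresponding positive sclerotic lesion on the CT portion of the" PET. No condition on the age of any earlier scan.
- Baseline bone scan: "If there is focal uptake seen on the baseline bone scan performed within one month of" the PET.
- Initial MRI: "If there is a lesion noted on the initial MRI performed within one month of" the PET.
- Follow-up CT: sclerosis develops within 12 months.
- Follow-up MRI: "If within 12 months follow-up MRI demonstrates a new bone lesion".
- Follow-up bone scan: "If within 12 months follow-up bone scan demonstrates new focal uptake".

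The false-positive rule is a catch-all. It applies whenever PSMA-"positive bone lesions do not meet the criteria for true positive findings". There is no indeterminate class.

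The other tissue types are treated differently. Visceral and prostate-bed lesions are true positive if they decrease under treatment "or increase by 20% in largest diameter". Nodes are credited for an increase of more than 20% in short axis, with a change of at least 3 mm.

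On the choice of follow-up scan, 8.3.2 b) states: "The follow-up conventional imaging should be the same modality/modalities as the initial staging work-up to allow for reproducible and accurate comparisons".

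**The concern.** The bone-scan and MRI criteria leave a gap between them. Evidence from around the time of PET expires at one month, and follow-up evidence counts only if it is new. A lesion first seen on an older scan and larger at follow-up falls between the two, although visible progression is the kind of non-histological confirmation that the plan accepts in every other region.

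Nothing in the plan keeps patients inside the window. The schedule in 6.1 has no row for conventional imaging, and the screening list in 6.1.1.1 covers PSA, pathology and performance status only. The age of the bone scan or MRI is therefore left to routine care. Bone is also the region to which 8.2.1 gives the largest share of disease, 35%.

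At stake are the bone and per-patient PPVs under the combined histology and imaging reference (8.3.3). Section 8.3.2 c) also sends indeterminate bone biopsies to these same imaging rules.

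**Working it through.** **The rule applied to four cases.** In each, the lesion is PSMA-positive, not sclerotic on the index CT and not sclerotic on follow-up CT, so both CT routes are closed. Newness is judged against the earlier scan.

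| Case | Before PET | Follow-up | Score |
|---|---|---|---|
| A | Bone-scan uptake, 28 days | Unchanged | True positive (in window) |
| B | Bone-scan uptake, 35 days | Larger | False positive |
| C | MRI lesion, 45 days | Doubled on MRI | False positive |
| D | Nothing seen | New uptake on bone scan | True positive (new) |

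B and C fail the baseline criteria on date and the follow-up criteria because the finding is not new. The catch-all then applies. A visceral or prostate-bed lesion that doubled in diameter would pass its 20% criterion. Case A passes with no follow-up evidence at all, while B, with documented growth, fails.

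**The plan's own figure.** Section 8.2.1 gives bone 375 × 0.35 = 131.25, shown as 131, with power above 99% for PPV 50% against 70% at one-sided 0.01. By normal approximation:

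Φ[(0.20 × √131 − 2.326 × √0.25) / √0.21] = Φ[(2.289 − 1.163) / 0.458] = Φ(2.46) = 99.3%.

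The stated figure reproduces. It belongs to the histopathology analysis, which these imaging rules enter only through indeterminate bone biopsies.

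**What a given error rate would cost.** Let m be the share of truly positive bone regions that this gap turns into false positives. The denominator, all PET-positive bone regions with a verdict, does not change. Taking 70% (the alternative in 8.2.1) as the true PPV and assuming no other classification error:

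reported PPV = 0.70 × (1 − m)

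- m = 1%: 69.3%
- m = 5%: 66.5%
- m = 10%: 63.0%
- m = 20%: 56.0%
- m = 28.6%: 50.0%, the null value in 8.2.1

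This converts m into PPV and does not predict it. To estimate m one would need the distribution of scan age at PET, the share of true lesions visible on bone scan or MRI but not sclerotic, the share of those that stay non-sclerotic, and the share that grow. The documents give none of these.

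**The case against.** The case against has several parts, and much of it stands.

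- **The CT routes rescue many lesions.** A reader might infer that any bone metastasis first seen on an older scan is scored false positive. The text does not support that: a sclerotic correlate on the index CT, or sclerosis developing later, makes the lesion true positive whatever the age of earlier scans. With PET/MRI, which 3.1 allows, there is no CT portion. The plan does not say whether the MRI component then counts as the initial MRI; if it does, the gap narrows.
- **The wording is partly open.** 'New' has no stated reference scan. If it means new since a scan inside the window, some cases are rescued. The request for the same modality at follow-up makes comparison with the older scan natural, but does not prescribe it. The one-month limit is also not expressly restricted to scans before PET. These ambiguities shrink the gap under some readings; they also let sites classify the same lesion differently.
- **One lesion need not decide the region.** A region is read as positive if at least one lesion is, so another qualifying bone lesion could still validate it.
- **The net bias is unknown.** A sclerotic correlate, or an in-window MRI lesion, counts as true positive without further confirmation. Those lenient routes could raise the reported PPV. The direction is known only for the lesions described here.
- **The primary analysis is largely untouched.** It rests on histopathology, and for negative biopsies 8.3.2 c) also allows repeat PET and repeat conventional imaging.

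None of this supplies a true-positive route for a growing, non-sclerotic lesion compared with an out-of-window scan.

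**Conclusion.** The concern holds in this limited form. It requires that the lesion is not sclerotic on the index CT (or there is no CT portion), does not become sclerotic on follow-up CT, has no qualifying in-window bone scan or MRI, is not settled by biopsy, and that newness is judged against the older scan. Such a lesion is scored false positive even when it grows. The consequence is mainly for the secondary combined-reference PPV.

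A reader might want an expected figure for the depressed bone PPV, or a count of affected regions. Neither can be derived. Any such count would have to assume how many unbiopsied patients are PET-positive in bone and have an informative earlier scan, and the schedule requires no such scan. The conversion above should not be quoted as a forecast.

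A reader might also infer that unchanged lesions should leave the main denominator. That does not follow: 8.3.2 c) itself names Paget's disease as a PSMA-positive alternative diagnosis, so excluding unchanged lesions could remove genuine false positives and raise the PPV.

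**What to change.** In 8.3.2 b) iii)(1), replace the follow-up MRI and bone-scan criteria with wording such as: 'within 12 months, follow-up MRI or bone scan shows, at the PET-positive site, a lesion or uptake that is new, or has increased by the prespecified amount, compared with the last pre-PET scan of the same modality.' This also fixes the reference scan for 'new'.

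Prespecify the increase before adjudication starts, because follow-up imaging is read locally and 8.1.1 states that there is no blinding. For lesions measurable on MRI, the 20% size increase already used for viscera and prostate bed is an obvious candidate. Bone-scan uptake needs its own definition.

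Keep the false-positive default for unchanged lesions in the main analysis. Add a sensitivity analysis for lesions visible on an out-of-window scan and unchanged at follow-up: first count them all as true positive, then exclude them. The one-month cut-off will still decide the class of unchanged lesions, and this analysis shows how much that matters.

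The cost is a rewording, one sensitivity analysis, slightly more adjudication and some reader judgement on what counts as an increase. No extra scans are needed, since 8.3.2 b) already plans conventional follow-up imaging for all patients at 3-12 months.
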